13 STUDY PROCEDURES

13.1 Subject Recruitment

Subjects will be recruited at the research centers at UVa and in San Diego and Houston. Recruitment strategies vary across each site based on their local population, however, standard tactics will be used (i.e., flyers, newspaper advertisements, radio advertisements, internet advertisements). Local IRBs will approve all advertising materials used for subject recruitment.

Interested candidates responding to recruitment materials by telephone will be asked a standardized set of questions about their drinking and smoking behavior without revealing the entry criteria into the study and will be asked if they are seeking treatment and are available for approximately 8 months. Candidates will additionally be asked if they are willing to quit both smoking and drinking within the next 30 to 60 days.

Candidates who report drinking and smoking consistent with the entry criteria, confirm their willingness to quit smoking and drinking, and appear to be available and interested in the study will meet with the investigator or designated investigational staff within 30 days after the initial inquiry to start the informed consent process and assessment process.

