13.3 Subject Randomization

Prior to randomization, data essential for eligibility will be reassessed. Drinking and smoking requirements during the time period between the screening visit and visit 1 will be reassessed. All essential data for assignment to a treatment group will be collected by the study staff on the randomization form.

Assignment to a stratum during randomization will be based on the following: age of onset (≤ 25 or >25), drinks per drinking day (DDD) during the 90 days prior to screening (<8 or ≥ 8), average number of cigarettes smoked per day during the 90 days prior to screening, and gender. Calculations will be made using the formulas below.

$$\frac{\text{90 Day SDU Total}}{\text{\# Drinking Days}} = \text{Drinks per Drinking Day (DDD)}$$

$$\frac{\text{90 Day Cigarette Total}}{\text{90 Days}} = \text{Average \# Cigarettes per Day}$$

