Primary Outcomes Analytical Models:

We will use generalized linear models (GLM) to estimate treatment effects on PHDD and logistic regression for abstinence. We will adjust for baseline covariates on the same drinking or smoking variables. For the drinking and smoking variables, that baseline is the averaged value for the 90-day period prior to the screening visit. Other potential covariates shall include age, gender, and ethnicity. We also will consider the treatment period up to the TQD as an additional set of covariates for analyses that focus on the last 4 weeks of treatment. The residuals from our analyses will be checked for normality by computing their skewness and kurtosis and will be checked for homogeneity of variance by plotting them in a histogram and against predicted outcomes. Standard transformations will be employed to improve the distributions when required (i.e., square root or log transformation).

If, however, there is a differential attrition rate (i.e., if dropout is informative), we shall consider other approaches to handle repeated-measures data that can be adopted to obtain valid results.[7, 8]

Exploratory Analytical Models:

We also will use the more advanced two-part random-effects model[9, 10] to analyze the daily drinking and smoking record. Such a model can simultaneously characterize the frequency (odds of daily drinking or smoking being zero) and quantity (number of drinks on a drinking day or number of cigarettes smoked on a smoking day) of drinking and smoking outcomes, respectively. It is more efficient and can tackle non-normality in the drinking or smoking level. We also are interested in trajectory analysis of different treatments over time to capture differences in these outcomes. Such analysis is more clinically intuitive and could be more powerful than the analysis based on endpoint.

The Kaplan-Meier survival method will be used to compare time to achieve continuous abstinence between the treatment groups. Homogeneity between different arms will be tested with the log-rank test. Additionally, we will use the Cox proportional-hazards model to estimate the relative likelihood (i.e., magnitude of the treatment response) between the treatment groups for achieving continuous periods of abstinence. For the Cox regression model, potential confounding variables such as age of onset for alcoholism (less than 26 years old or 26 years and

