15.5 Sample Size Calculation

We did two sets of power analysis to account for the drinking and smoking endpoints in our proposed study. Importantly, because smoking outcomes are based mostly on dichotomous variables, power estimates for these outcomes drive the numbers needed for this comorbid alcohol- and nicotine-dependent cohort. Hence, it is important to have adequate power for the smoking outcomes even though this will result in a superfluous level of power for the drinking outcomes.

First, for the smoking outcomes, we did a power analysis by comparing the two-sample difference in nicotine abstinence using SAS Proc POWER. We have estimated power based upon our ability to detect a difference in the percentage of smoking abstinence between the treatment groups. Because the comparisons of the topiramate groups with one another (i.e., high vs. low) and with placebo are experimental, we chose to calculate power to detect the effect size of therapeutic treatments typical of the smoking cessation literature. We chose to calculate power based on our estimates of the percentage of smoking abstinence in the pivotal study by Jorenby et al.,[72] where bupropion was compared with placebo in a 9-week randomized, controlled clinical trial. In that study, the TQD occurred at the end of the first week of double-blind treatment. As a conservative measure, we have accepted the subject numbers for these two groups for the present study to represent the comparison of the low-dose topiramate vs. placebo or the high-dose vs. low-dose topiramate. Thus, we have assumed that the difference between low-dose topiramate and placebo would be similar to that between high- and low-dose topiramate. Since there are 3 pairwise comparisons between the three arms, we will adopt Bonferroni's adjustment and take alpha level as $0.05/3 = 0.017$.

From Figure 1 in Jorenby et al.,[72] the continuous prevalence rate of smoking abstinence at 18 weeks is approximately 10% for placebo and 28% for bupropion. Using these numbers, we find that 98 subjects in each arm (294 in total) are needed to achieve a power of 0.80. If we observe a similar effect to that in the preliminary study we will be operating under even increased power.

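### Site is not pre-specified in either primary model of this three-centre trial; its absence causes no bias, but adding it is a cheap way to gain a little power if site is prognostic.

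*Combined protocol and SAP*

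**What the plan says.** Section 13.1 states: "Subjects will be recruited at the research centers at UVa and in San Diego and Houston".

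Section 15.4, under Primary Outcomes Analytical Models, sets the analysis: "We will use generalized linear models (GLM) to estimate treatment effects on PHDD and logistic regression for abstinence". On covariates it commits to one item, "We will adjust for baseline covariates on the same drinking or smoking variables", and then offers two further sets:

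- "Other potential covariates shall include age, gender, and ethnicity"
- data from the weeks on treatment before the target quit date, as an option when the final four weeks are analysed.

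Site is in none of these. Section 13.3 opens its list of strata with "Assignment to a stratum during randomization will be based on the following" and names age of onset, drinks per drinking day, cigarettes per day and gender. The Abstract and section 9 give the same four factors. Site is also missing from the exploratory Cox covariates in section 15.4 and from the sample size calculation in section 15.5. Section 15.4 says that the general approach follows two earlier trials, but not whether their models had a site term.

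**The concern.** There is some reason to expect outcomes to differ by centre. Section 13.1 says "Recruitment strategies vary across each site based on their local population", and counselling is given by research staff at each centre. If centres do differ, leaving site out has two effects. In the PHDD model the between-site variation stays in the residual and widens the standard error. In the logistic model it pulls the estimated log odds ratio towards zero and lowers power. Because site is not a listed stratum, the mix of sites can also differ between arms by chance.

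The smoking outcome matters more here. Section 15.5 says that it drives the sample size, and its calculation gives 80% power with nothing in reserve.

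**Working it through.** **1. The plan's own figure.** Inputs from section 15.5: abstinence 10% and 28%, alpha 0.05/3 rounded to 0.017, power 0.80. Sidedness is not stated; two-sided is assumed. With pooled variance under the null:

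n = [z(α/2)·√(2·p̄·(1−p̄)) + z(0.80)·√(p₁(1−p₁) + p₂(1−p₂))]² / (p₂−p₁)²

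Here p̄ = 0.19, so n = [2.387·√0.3078 + 0.842·√0.2916]² / 0.18² ≈ 97.7, which rounds up to 98 per arm as stated. With alpha unrounded it is 99. The calculation is an unadjusted two-sample comparison without a site term. The 76 per arm for drinking cannot be rebuilt, because the earlier trial's size and the mixed-model degrees of freedom are not given.

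**2. PHDD model.** Let R² be the share of residual variance explained by site (assumed). The standard error is multiplied by √(1−R²). For a comparison that has 80% power without site, the new power is Φ[(z(α/2) + z(0.80))/√(1−R²) − z(α/2)], with alpha = 0.05/3.

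| R² | SE ratio | Power with site | n per arm giving the original power, 98·(1−R²) |
|---|---|---|---|
| 1% | 0.995 | 80.4% | 97.0 |
| 2% | 0.990 | 80.9% | 96.0 |
| 5% | 0.975 | 82.3% | 93.1 |
| 10% | 0.949 | 84.5% | 88.2 |

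Over the trial, 2% to 5% is worth about 6 to 15 participants (294 × 0.02 = 5.9; 294 × 0.05 = 14.7).

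**3. Smoking logistic model.** Simulation: two arms of 98, three sites of equal expected size, allocation not stratified by site, overall rates 10% and 28%, alpha 0.05/3, 4,000 runs per row, no other covariates. The site spread is assumed.

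| Control rate by site | Power without site | Power with site | Mean SE of log OR, without → with |
|---|---|---|---|
| 10/10/10% | 0.810 | 0.806 | 0.419 → 0.422 |
| 7/10/13% | 0.802 | 0.805 | 0.419 → 0.425 |
| 5/9/17% | 0.807 | 0.825 | 0.417 → 0.431 |
| 3/8/19% | 0.806 | 0.845 | 0.419 → 0.442 |

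The standard error rises when site is added. Power also rises wherever sites differ, because the estimate moves further from zero (median log OR 1.273 → 1.349 in the 5/9/17% row). Each power figure has a simulation error of about √(0.8·0.2/4000) = 0.6 points. Both models were fitted to the same data sets, so the differences are steadier than that.

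**4. Type I error.** Under the null, rejection without and with site was 0.011 and 0.011 (no site effect), 0.011 and 0.012 (5/9/17%), and 0.009 and 0.010 (3/8/19%), against a nominal 0.0167.

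**5. Chance imbalance.** With three equal sites and no site stratum, the SD of the between-arm difference in one site's share is √(2·(1/3)(2/3)/98) = 6.7 points. In simulation about 32% of trials differed by more than 10 points at some site. The resulting shift in the abstinence difference has SD 0.3, 0.6 or 1.2 points for a site spread of 5, 10 or 20 points. The total standard error of that difference is √(0.2916/98) = 5.5 points.

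**The case against.** The case against is substantial, and most of it limits the size of the point.

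- **The evidence for a site effect is thin.** The sentence in section 13.1 about differing recruitment goes on to say that standard methods will be used. Eligibility is common to all centres. Section 12.2 requires certified counsellors, central review of about 10% of recorded sessions and coordinated supervision. Section 14.18 has one coordinating centre train all sites on the timeline follow-back. Baseline adjustment would also absorb part of any difference in case mix. All of this stands. It makes a large site effect less likely without ruling one out.
- **The drinking outcome has power to spare.** Section 15.5 needs 76 per arm for it and enrols 98, so the PHDD gain is worth less than the table suggests. This stands.
- **Placebo events are few.** At 10% of 98 there are about 10 abstainers, or roughly three per site. Two more parameters are not free, as the 0.4-point loss with no site effect shows.
- **The covariate list is only potential.** Site is therefore not forbidden. But that leaves its inclusion undecided until data are in hand, which is a reason to settle it now.

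A reader might infer that the omission lets site imbalance bias the treatment effect. The documents do not support that: allocation is random, the shift is chance error that the unadjusted standard error already contains, and rejection under the null stayed below nominal. A reader might also infer that allocation is blocked within site, which would make the unadjusted PHDD standard error too large. The sections on randomisation do not describe this. Section 8 (Study Sites) could not be read for this point.

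**Conclusion.** The point holds as a cheap improvement and no more. Three centres recruit, and neither primary model nor the listed strata name site. The validity of the primary tests is not in question.

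The possible gain is about 1 to 2 points of power for PHDD if site explains 2% to 5% of residual variance, starting from 80%. For smoking it is nil to about 4 points, and reaches 2 points or more only when site control rates spread at least as widely as about 5/9/17%. Every one of these site effects is assumed; the documents supply none. The smoking figures further assume equal sites, no dropout and no other covariates.

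A claim that adjustment improves precision would be right for PHDD. It would be wrong for the log odds ratio, where the benefit is power only.

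**What to change.** In section 15.4, state that both primary models will include treatment group, the 90-day baseline value of the outcome, and site as a fixed effect with three levels. Say that site stays in the model whatever its own p-value, and that the odds ratio for abstinence is then conditional on site.

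This is one line in the plan and needs no new data, since section 11.2 already has the site number printed on each medication bottle. The statistical cost is two degrees of freedom and the small loss of smoking power shown above if site turns out not to matter.

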Absorption of topiramate is rapid, with peak plasma concentrations occurring at approximately 2 hours following a 400 mg oral dose. The relative bioavailability of topiramate from the tablet formulation is about 80% compared to a solution. The bioavailability of topiramate is not affected by food.

The pharmacokinetics of topiramate are linear with dose proportional increases in plasma concentration over the dose range studied (200 to 800 mg/day). The mean plasma elimination half-life is 21 hours after single or multiple doses. Steady state is thus reached in about 4 days in patients with normal renal function. Topiramate is 15-41% bound to human plasma proteins over the blood concentration range of 0.5 -250 μ g/mL. The fraction bound decreased as blood concentration increased.

5.2.4 *Adverse Effects*

Topiramate at the dosage that will be prescribed in this proposal is well tolerated. The most common adverse events (AEs) that we observed in our alcohol treatment study were transient tingling, psychomotor slowing, weight loss, and dizziness. We acknowledge that other central nervous system adverse events have been reported by others, such as ataxia, speech disorders and related speech problems, cognitive slowing, mood disturbance, and nystagmus (eyes jumping), but these would appear to be more manifest at higher doses than what we have proposed. A rarer adverse event of topiramate is kidney stone, which was not seen in any of our previous studies. Topiramate has weak carbonic anhydrase properties. Thus, topiramate's concurrent use with other carbonic anhydrase inhibitors, such as acetazolamide and zonisamide, may increase the risk of kidney stone formation and should, therefore, be avoided. Topiramate may be associated with the development of metabolic acidosis.

Psychological risks can include distress and heightened sensitivity, which can occur as part of the behavioral treatments, clinical interviews, or completing self-reported ratings and questionnaires. While the possibility of such events is low, we will monitor these situations and provide an appropriate level of support. Such events will be documented fully in the case records.

5.2.5 *Withdrawal*

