9 STUDY DESIGN

Two hundred and ninety-four comorbid nicotine-dependent subjects with mild to severe alcohol use disorder who meet eligibility criteria will be randomized to 1 of 3 treatment groups — placebo, low-dose topiramate (up to 125 mg/day), or high-dose topiramate (up to 250 mg/day). Randomization will be achieved using a block randomization procedure in which treatment groups will be stratified to achieve a balance on age of onset for alcoholism (less than 26 years old or 26 years and older), gender, and drinks per drinking day (DDD) (<8 DDD or ≥ 8 DDD) and the number of cigarettes smoked (<20 or ≥ 20 cigarettes/day).

Following randomization, subjects will participate in an 18-week, double-blind treatment period during which they also will receive weekly BBCET, and a self-help manual for smoking cessation. Topiramate and matching placebo will be titrated for the first 5 weeks of the 18-week treatment period. The TQD will be at the beginning of the 6th week of treatment. Subjects will be instructed not to attempt smoking or alcohol cessation prior to the TQD. Setting a TQD at the end of medication titration enables stability of effects, comfort with the medication prior to attempting to cease alcohol and smoking consumption, and an appreciable buildup of medication. However, in cases where individuals either quit smoking or alcohol consumption prior to the TQD, counseling will be directed at helping them maintain their abstinence and reengaging their efforts in the event of relapse. If an individual finds that he or she cannot quit

smoking and/or consuming alcohol completely following the TQD, he or she shall remain in the study and counseling will be directed at the continued setting of reduction goals, with cessation as the ultimate target.

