12 INTERVENTIONS

12.1 Investigational Agents

Topiramate will be self administered by subjects in a dosing regimen of one capsule in the evening beginning on Day 1, Week 1 and then moving to one capsule in the morning and one capsule in the evening beginning on Day 8, Week 2 and continuing through Day 126, of Week 18.

The titration scheme has been devised such that this process is completed for the low- or high-dose topiramate groups, and matching placebo, at the end of week 5 (i.e., beginning of week 6). Both titration schemes are provided below:

Topiramate high-dose escalation schedule

Week	A.M. Dose	P.M. Dose	Total Daily Dose
1	-	50 mg	50 mg
2	50 mg	50 mg	100 mg
3	75 mg	75 mg	150 mg
4	100 mg	100 mg	200 mg

5	125 mg	125 mg	250 mg
6-18	125 mg	125 mg	250 mg

Topiramate low-dose escalation schedule

Week	A.M. Dose	P.M. Dose	Total Daily Dose
1	-	25 mg	25 mg
2	25 mg	25 mg	50 mg
3	37.5 mg	37.5 mg	75 mg
4	50 mg	50 mg	100 mg
5	62.5 mg	62.5 mg	125 mg
6-18	62.5 mg	62.5 mg	125 mg

Missed Doses. If a subject misses a week or more of investigational products, the product may be re-introduced with the A.M. dose for two days, then only the P.M. dose for the following two nights and by day 5 both doses should be taken, if tolerated. If a subject misses up to 6 consecutive days' doses, s/he will be instructed to start taking the investigational product at the last dose that s/he was taking before stopping. If the subject realizes he/she missed the AM dose and it is after 12pm then the subject should not take missed AM dose. A missed AM dose can be taken anytime before 12pm of the same day. If the subject realizes he/she missed the PM dose and it is the next day then the subject should not take missed PM dose. A missed PM dose can be taken before 24:00 (midnight) of the same day.

Medication Management. Pills may be taken with or without food. If a subject cannot tolerate a dose, the dose will be de-escalated to the next lower tolerated dose and a new kit will be ordered from Greenpark Compounding Pharmacy. Until the new kit arrives, subjects will take only one of their two daily pills. On an as needed basis and with the judgment of the site PI, both doses can be moved to the PM to manage sedation.

Placebo Control: Subjects assigned to the placebo group will receive the same number of matched placebo capsules on the same schedule as the topiramate high-dose and low-dose groups.

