15 ANALYTICAL PLAN

15.1 Outcome Measures

The primary efficacy variables will be the PHDD for the drinking outcome and the continuous abstinence rate for the smoking outcome (during the last 4 weeks of treatment, i.e., weeks 15–18 inclusive), respectively. The secondary efficacy variables will be quality of life and measures of alcohol and nicotine craving. Exploratory outcomes include measures of dependence, and measures of nicotine and alcohol withdrawal including negative effect, as noted below:

1. Fagerström Test for Nicotine Dependence
2. Revised Clinical Institute Withdrawal Assessment for Alcohol scale (CIWA-Ar) [2]
3. Wisconsin Smoking Withdrawal Scale
4. Positive Affect Negative Affect Schedule (PANAS)
5. The Center for Epidemiologic Studies Depression Scale (CES-D)
6. Medical Outcomes Sleep Scale (MOS-Sleep)
7. The Drinker Inventory of Consequences (DrInC)[3]

Additional exploratory outcome variables will include other: 1) measures of drinking severity (i.e., DDD) and abstinence (i.e., percentage of days abstinent; PDA) averaged across either the entire double-blind period or the last 4 weeks of treatment, and 2) smoking measures including the point prevalence abstinence rate and the CO level over either the entire double-blind period or the last 4 weeks of treatment.

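### Section 15.4 leaves open adjusting the primary weeks 15–18 PHDD result for on-drug weeks 1–5, which would move it off the intention-to-treat effect if the drug acts before the target quit date

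*Combined protocol and SAP*

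**What the plan says.** Section 15.4, under Primary Outcomes Analytical Models, plans a generalized linear model for PHDD and logistic regression for smoking abstinence. The firm adjustment is "We will adjust for baseline covariates on the same drinking or smoking variables", with baseline taken as the average over the 90 days before screening. Then: "Other potential covariates shall include age, gender, and ethnicity". For analyses of the last 4 weeks it adds: "We also will consider the treatment period up to the TQD as an additional set of covariates". It does not say which weeks 1–5 variable is meant, what would trigger its use, or which fitted model supplies the primary result. A separate exploratory heading follows, and this sentence is not under it.

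The primary window is "during the last 4 weeks of treatment, i.e., weeks 15–18 inclusive" (section 15.1; likewise sections 6.1 and 15.4). The primary population is all randomised subjects.

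On timing, section 12.1 states: "Topiramate will be self administered by subjects in a dosing regimen of one capsule in the evening beginning on Day 1, Week 1". Section 9 places titration in weeks 1–5 and the TQD at the start of week 6. It gives this reason: "Setting a TQD at the end of medication titration enables stability of effects, comfort with the medication". It also says: "Subjects will be instructed not to attempt smoking or alcohol cessation prior to the TQD", and then provides for people who do stop drinking or smoking early.

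Randomisation is stratified on age of onset, gender, drinks per drinking day and cigarettes per day (sections 9 and 13.3). Age of onset is named as a possible covariate only for the exploratory Cox model.

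**The concern.** The hypotheses in section 15.3, tested in all randomised subjects, concern the total effect of assignment on late drinking. A pre-randomisation covariate leaves that target unchanged in the PHDD model. Drinking in weeks 1–5 is different: treatment can already have changed it. Once it is in the model, the arms are compared at equal early drinking, and any early benefit that persists is subtracted from the late result. The subtraction happens even if early and late drinking are linked only because people differ stably from one another.

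The plan therefore leaves two different quantities available for one primary PHDD result, with no rule for choosing between them. For smoking, the objection to a post-randomisation covariate is the same in principle, but the documents give nothing from which to size it.

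A lesser matter is that the named primary covariates do not cover all the factors used to stratify randomisation.

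**Working it through.** **1. The plan's own figure.** For 10% versus 28% abstinence, power 0.80, two-sided, pooled variance and no continuity correction, the sample size is 98 per arm at alpha 0.017 (99 at 0.05/3). The stated 98 is reproduced, and this point does not change it. The 76 per arm for drinking cannot be checked, because the earlier trial's size is not given.

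**2. Formula.** Let E be the arm difference in mean PHDD over weeks 1–5 and L the difference over weeks 15–18. Let b be the within-arm slope of late on early PHDD, given baseline.

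- Baseline-only model estimates L.
- Model with weeks 1–5 added estimates L − b × E.
- Share of L removed = b × E/L.

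**3. Inputs.** Section 15.5 gives a PHDD slope difference of 0.014 per week from an earlier topiramate trial, with no onset or shape. The titration tables give mean weeks 1–5 doses of (50+100+150+200+250)/5 = 150 of 250 mg and (25+50+75+100+125)/5 = 75 of 125 mg. Both are 60% of target. The values of b and the shape of the effect are assumptions.

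**4. Results.**

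| Assumed shape | E/L | Removed, b 0.3–0.7 | Removed, b 0.9 |
|---|---|---|---|
| No effect before the TQD | 0 | 0% | 0% |
| 0.014 per week, linear from the start | 0.042/0.231 = 0.18 | 5.5–12.7% | 16.4% |
| Effect proportional to titrated dose | 0.60 | 18–42% | 54% |

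In the linear row, E = 0.014 × 3 (the mean of weeks 1 to 5) = 0.042, and L = 0.014 × 16.5 (the mean of weeks 15 to 18) = 0.231. The adjusted effect is 0.231 − 0.3 × 0.042 = 0.218 at b = 0.3 and 0.231 − 0.9 × 0.042 = 0.193 at b = 0.9.

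**5. Check with baseline in the model.** A simulation of 400,000 subjects per scenario assumed correlations of 0.5 (baseline–early), 0.4 (baseline–late) and 0.5 or 0.7 (early–late). These imply b = (0.5 − 0.5 × 0.4)/(1 − 0.5²) = 0.40 or (0.7 − 0.2)/0.75 = 0.67. The share removed was about 0% at E/L = 0, 7–12% at 0.18 and 24–40% at 0.60, which agrees with the formula.

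**6. Power.** With an assumed late effect of 0.4 SD, 98 per arm and alpha 0.05/3, the baseline-only model has power of about 0.73–0.76. Adding weeks 1–5 gives 0.82–0.94 at E/L = 0, 0.75–0.86 at 0.18 and 0.48–0.54 at 0.60. The covariate reduces residual variance as well as the effect, so power can go either way.

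**7. Randomisation factors.** The named primary covariates omit age of onset and the other substance's stratum, and gender is only potential. If the omitted factors explained 2–10% of residual PHDD variance (an assumption), the standard error would be 1/√0.98 = 1.010 to 1/√0.90 = 1.054 times what it need be. This is an upper figure: it takes balance as complete across 2⁴ = 16 strata of about 294/16 = 18 subjects.

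**The case against.** The sentence only says the team will consider this, and the firm baseline adjustment beside it is sound. Harm requires that the option is taken, that the result is reported as primary, that the covariate is early drinking, and that the drug acts before the TQD. The documents do not show the last of these. Subjects are told not to attempt cessation before the TQD, and its timing is justified partly by drug build-up. Section 5.2.3 says "Steady state is thus reached in about 4 days in patients with normal renal function", but that describes plasma levels, not drinking. Under the linear reading the shift is modest, power is about equal or higher, and the shift is toward a smaller drug effect.

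Most of this stands, and it makes the point conditional. It does not remove it. PHDD can fall without cessation, section 9 itself provides for early quitters, and no section confines the option to a sensitivity analysis or names the baseline-only model as primary.

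A reader might infer that the plan commits to this adjustment, or that it must cost power. The text supports neither. A reader might also take the subtracted amount to be the part of the effect mediated through weeks 1–5. It is only slope times early effect, and would equal a mediated part only if early and late drinking shared no unmeasured causes beyond the covariates. Nor does the linear row set an upper limit: it holds only for a difference that keeps growing by 0.014 a week.

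On the lesser matter, the list of potential covariates is open-ended, so the missing factors are unnamed, not excluded.

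**Conclusion.** The point holds conditionally. If weeks 1–5 drinking enters the primary PHDD model and the drug acts before the TQD, the reported figure falls short of the intention-to-treat effect for any positive b. If the drug has no effect before the TQD, the estimate is unchanged.

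The plausible size runs from nothing, through about 5–16% on a linear reading of the plan's own slope, to 18–42% if effect follows dose. This range reflects assumptions about b and onset and is not an estimate. It supports no claim about the sample size, the direction of any change in power, or the size of any effect on smoking.

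The incomplete naming of randomisation factors is minor. For PHDD it costs some precision without bias. For the logistic model it also changes which conditional odds ratio is estimated.

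**What to change.** In section 15.4, state that the primary models use pre-randomisation covariates only, and fix the list before unblinding: the 90-day baseline of the outcome variable plus the four randomisation factors, without repeating a factor already represented by its continuous baseline.

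- PHDD: baseline PHDD, drinks per drinking day, cigarettes per day, age of onset, gender.
- Smoking: baseline cigarettes per day, drinks per drinking day, age of onset, gender.

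Age and ethnicity also precede randomisation. Nothing here argues against keeping them, provided the same list settles it. Move any adjustment for the treatment period up to the TQD to a labelled exploratory analysis, and name the variable used.

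The cost is one sentence moved and one list fixed. The randomisation factors are already collected, and sample size and visits do not change. The downside is possibly a few more terms in a logistic model with few abstainers. At 10% versus 28% of 98, a low-dose versus placebo comparison has 9.8 + 27.4 = about 37 abstainers. With treatment and the four smoking covariates that is 37.2/5 = 7.4 per term. The plan's own baseline, age, gender, ethnicity and treatment would already make at least five terms.
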